7.2 Registration

Registrations will be provided electronically.

Note: The validity of results of the trial depends on the authenticity of and the follow-up of all patients entered into the trial. Under no circumstances, therefore, may an allocated patient's data be withdrawn prior to final analysis, unless the participant withdraws from the trial and requests that data collection/submission cease from the point in time of withdrawal.

All eligible patients admitted to the trial will be followed by the coordinating centre. It is the responsibility of the physician in charge to satisfy himself or herself that the patient is indeed eligible before requesting registration.

All patients are to be followed until death or until sites are informed by CCTG that further follow-up is no longer required.

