9.0 EVALUATION DURING AND AFTER PROTOCOL TREATMENT

All patients entered on study must be evaluated according to the schedule outlined in Appendix I with documentation submitted according to the schedule in Appendix IV.

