9.2 Evaluation After Protocol Treatment

All patients will be seen at 4 weeks after the end of the last cycle date. Thereafter, continued follow-up is not required for patients who go off protocol treatment with progressive disease, except to document ongoing toxicities (until resolved to \leq grade 2) and late toxicities (including second malignancies). Patients who go off protocol therapy before progression is documented or have objective CR, PR or SD ongoing, follow-up and a Follow-up Report will be required at least every 3 months for a maximum of 1 year, (See Appendix I for investigations to be performed). Death Report will be required for all patients. Due within 2 weeks of knowledge of death (see Appendix IV - Documentation for Study).

Investigations		Timing
History and Physical Exam including:	
 history weight ECOG Performance status vital signs (blood pressure and pulse) clinical tumour measurements (if applicable) 	4 weeks post end of last cycle
Hematology	
 CBC, differential, platelets 	4 weeks post end of last cycle
Biochemistry	
 electrolytes (sodium, potassium, chloride, bicarbonate) alkaline phosphatase AST, ALT serum creatinine bilirubin 	4 weeks post end of last cycle
	
 phosphorous calcium magnesium albumin 	As clinically indicated
Radiology*	
 CT with contrast of chest, abdomen and pelvis 	As per standard of care (at least every 3 months) until progression or a maximum of 1 year
Other Investigations	
 ECG 	As clinically indicated
Adverse Events	Adverse events will be recorded and graded according to the NCI Common Terminology Criteria for Adverse Events (CTCAE) (Appendix V).	4 weeks post end of last cycle
* Patients with a CR or PR should have scans repeated after minimum 4 weeks to confirm response.		

AMEND #1: 2016-NOV-23

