12.4 Follow-up Off Protocol Treatment

See Section 9.2.

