APPENDIX I - PATIENT EVALUATION FLOW SHEET

Required Investigations	Pre-study (within 7 days prior to registration, or as noted)	Day 1 each cycle	As clinically indicated	Every 12 weekly visit	4 wks, 12 wks then every 12 weeks	4 Weeks post treatment
History & Physical Exam						
Height and Weight	X ¹	X				X
ECOG Performance Status	X ¹	X				X
Vital signs (blood pressure and pulse)	X ¹	X				X
Documentation of all measurable and non-measurable disease	X ¹				X	X (if applicable)
Clinical tumour measurements (if applicable)	X ¹	X			X	X (if applicable)
Hematology & Biochemistry²						
CBC, differential, platelets	X	X				X
Serum creatinine, sodium, potassium, chloride, bicarbonate, bilirubin, ALP, AST, ALT, LDH ³ ,	X	X				X
Phosphorous, calcium, magnesium, albumin	X		X			
TSH, FT3, FT4	X	X ⁴				
HCV, HBV screening serology (if unknown)	X					
Other Investigations						
Pregnancy test, in women of childbearing potential only	X					
ECG	X ⁵		X			
Economics						
Health Utilities Index (EQ-5D)	X			X ⁶		
Resource Utilization Assessment				X ⁶		
Radiology						
CT scan with contrast of chest, abdomen/pelvis Other sites as clinically indicated	X (within 28 days prior to registration; 35 if negative)				X ⁷	X ⁸
Adverse Events						
Adverse Events/ Baseline Symptoms ⁹	X			Continuously each visit		X
1 Within 14 days prior to registration.						
2 Bloodwork Timing: Pre-treatment blood draws should be done within 72 hours (maximum) prior to treatment.						
3 LDH is not required after baseline.						
4 Every other cycle						
5 Only required if not done within 6 months prior to registration						
6 Each 12 weekly visit until progression OR maximum 1 year from registration						
7 Patients with a CR or PR should have scans repeated after minimum 4 weeks to confirm response						
8 All patients will be seen at 4 weeks after the end of last cycle date. Thereafter, continued follow-up is not required for patients who go off protocol treatment with progressive disease, except to document ongoing toxicities (until resolved to \leq grade 2) and late toxicities (including second malignancies). For patients who go off protocol therapy before progression is documented or have objective CR, PR or SD ongoing, follow-up and a Follow-up Report will be required at least every 3 months for a maximum of 1 year. A Death Report will be required for all patients.						

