APPENDIX IV - DOCUMENTATION FOR STUDY

Follow-up is required for patients from the time of registration and will apply to all eligible and ineligible patients. This trial will use a web-based Electronic Data Capture (EDC) system for all data collection including SAE reporting (see section 11.0 for details regarding SAE reporting). For details about accessing the EDC system and completing the on-line Case Report Forms, please refer to the Data Management Guidebook posted on the IND.225 area of the CCTG web-site (www.ctg.queensu.ca).

Form	To be Completed/Submitted Electronically:	Supporting Documentation to be sent using Supporting Document Upload Tool ²
PATIENT ENROLLMENT FOLDER	Must be completed at time of registration to confirm eligibility.	
BASELINE REPORT	Due within 2 weeks of patient registration.	Copies of signed consent signature page(s); relevant pathology and radiology reports; ECG reports
TREATMENT REPORT	To be completed every 3 weeks (i.e. after each cycle). Due within 2 weeks of end of cycle. This form documents treatment, adverse events, investigations and response assessment for each cycle.	Relevant radiology reports.
HEALTH UTILITIES INDEX (EQ-5D)	To be completed within 7 days prior to registration and at each 12 weekly visit until progression OR maximum 1 year from registration	Relevant radiology reports.
RESOURCE UTILIZATION ASSESSMENT	To be completed at each 12 weekly visit until progression OR maximum 1 year from registration.	Relevant radiology reports.
END OF TREATMENT REPORT	To be completed when patient goes off protocol treatment. Due within 2 weeks of end of protocol treatment.	
4 WEEK POST TREATMENT REPORT	To be completed once on all patients, 4 weeks after going off protocol treatment. Due within 2 weeks after contact with patient.	
FOLLOW-UP REPORT	Continued follow-up is not required for patients who go off protocol treatment with progressive disease , except to document ongoing toxicities (until resolved to \leq grade 2) and late toxicities (including second malignancies). For patients who go off protocol therapy before progression is documented or have objective CR, PR or SD ongoing, follow-up and a Follow-up Report will be required every 3 months for a maximum of 1 year. Due within 2 weeks after contact with patient.	Relevant radiology reports.

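### Section 10.8 gives no OS censoring rule for patients alive after progression, and the 9.2 follow-up waiver is not reconciled with 7.2 on survival status

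*Combined protocol and SAP*

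**What the plan says.** **Endpoint and censoring.** Section 1.2 lists OS among the secondary objectives, and Section 14.1 lists survival among the secondary endpoints. Section 10.7 runs OS from registration to death. Section 10.8 is the only censoring text. It covers patients who are alive and free of progression at the end of the study, and censors them at the last date on which both were known. Section 14 adds no OS censoring rule. Section 14.4 extrapolates this trial's survival in a Markov model.

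**Follow-up, general rule.** Section 7.2: "All patients are to be followed until death or until sites are informed by CCTG that further follow-up is no longer required". No interval, contact or form is attached. Three other places point the same way without a schedule: Section 5.1.10 (patients are to be followed at the participating centre), Section 12.1 (efforts to continue follow-up after early discontinuation) and the opening line of Appendix IV (follow-up applies to all eligible and ineligible patients).

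**Follow-up, schedule.** Section 9.2: "All patients will be seen at 4 weeks after the end of the last cycle date". Then: "Thereafter, continued follow-up is not required for patients who go off protocol treatment with progressive disease", except to document toxicity. Appendix I footnote 8 repeats this, and so does the Follow-up Report row of Appendix IV: "Continued follow-up is not required for patients who go off protocol treatment with" progressive disease. For patients who stop without progression, "follow-up and a Follow-up Report will be required at least every 3 months for a maximum of 1 year".

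**Which text sites are sent to.** Section 9.0 says patients "must be evaluated according to the schedule outlined in Appendix I with documentation submitted according to the schedule in Appendix IV". Section 12.4, on follow-up off treatment, reads in full: "See Section 9.2".

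**Deaths.** Section 9.2: "Death Report will be required for all patients. Due within 2 weeks of knowledge of death". Appendix IV footnote 1 makes the investigator responsible for investigating and reporting the date and cause of any death.

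**The concern.** The rule in 10.8 suits time to progression. For OS it leaves out patients who have progressed and are still alive. Their censoring date is undefined, and the schedule supplies no later contact from which to take one.

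The two kinds of information also arrive differently. A death after progression can enter the database whenever the site learns of it. A survivor who stopped with progression has no scheduled contact after the 4-week visit. If such survivors are censored at that visit while later deaths are counted at their true dates, survivors leave the risk set early, the denominators shrink, and the survival curve falls too fast. If instead some later deaths never become known, the curve is too high. Two centres could each follow the protocol in good faith and return different OS data, one reading 7.2 as governing survival and the other reading 9.2. Any error would carry into the life-years and QALYs of Section 14.4.

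**Working it through.** The plan states no OS sample size, event count or precision, so there is no figure to reproduce. The check is a comparison of texts, schedule arithmetic and an illustration.

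**1. Is there an OS date for each patient state?**
- Dead: date of death (10.7), through the Death Report (9.2, Appendix IV).
- Alive without progression: censored under 10.8.
- Alive after progression: no rule in 10.7, 10.8 or Section 14. Apart from toxicity follow-up and the Death Report, Appendix IV lists no survival contact or form after the 4-week report.

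**2. When does required contact end?** Inputs: 3-week cycles (8.1.1), CT at weeks 4 and 12 (9.1), last visit 4 weeks after the end of the last cycle (9.2). Doses fall at weeks 0, 3, 6, 9 and 12.
- Stops with progression at the week-4 CT: cycle 2 ends at week 6; 6 + 4 = week 10; 52 - 10 = 42 weeks to month 12 without scheduled survival contact.
- Stops at the week-12 CT: cycle 4 ends at week 12; 12 + 4 = week 16; 52 - 16 = 36 weeks. If cycle 5 was given: 15 + 4 = week 19; 52 - 19 = 33 weeks.
- Stops without progression: at most 12 months of treatment (12.2) plus 12 months of follow-up gives about month 24.

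These are early-stop cases. Section 10.2.5 lets clinically well patients continue past RECIST progression, with confirmation 4 to 8 weeks later, which moves the last contact back.

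**3. Illustration of size.** From the documents: n = 84 (14.2), and survival of 67% at 1 year and 50% at 2 years in a trial cited in Section 2. Everything else is assumed.
- A fraction p neither progresses nor dies. The rest have exponential time to progression (rate λ = ln 2 / median; median 2, 3, 4 or 6 months), then exponential survival after progression (rate μ = 1 / mean).
- OS at t months: S(t) = p + (1 - p)(μe^(-λt) - λe^(-μt)) / (μ - λ). Solving S(12) = 0.67 and S(24) = 0.50 gives p = 0.42 to 0.45 and a mean survival after progression of 10.4 months (median 2) down to 3.8 months (median 6).
- Check for median 2: λ = 0.347, μ = 1/10.4 = 0.096, p = 0.42. The fraction term at 12 months is 0.431, so S(12) = 0.42 + 0.58 × 0.431 = 0.67.
- Last contact is 7 weeks after progression (one 3-week cycle plus 4), or 15 weeks with an 8-week confirmation. Data cut-off is 18 or 24 months. Survivors who have progressed, and unreported deaths, are censored at last contact. There are 400,000 simulated patients per scenario, analysed by Kaplan-Meier.

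Results over all scenarios:
- Alive at month 12 but past last required contact: about 4 to 20 of 84.
- 12-month OS error, all later deaths reported: about -3.5 to 0 points. It is about -1.8 to 0 when median time to progression is 3 months or more.
- 75% of later deaths reported: about +0.6 to +3.6 points.
- 50% reported: about +3.6 to +8.2 points.
- Vital status complete to a common cut-off: 0.

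For scale, the standard error of 12-month OS is sqrt(0.67 × 0.33 / 84) = 0.051, or 5.1 points.

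**The case against.** The best defence is that the texts can be read together. Section 9.2 concerns visits and investigations, and the paragraph that holds the waiver also requires a Death Report for every patient, so visits and survival are already partly separated. Sections 7.2, 5.1.10 and 12.1 and the opening line of Appendix IV give a continuing duty under which the coordinating group could ask for vital status at a data cut without new authority. Censoring at the date last known alive is also conventional. This stands as far as it goes: a workable reading exists, and what is missing is the sentence that adopts it and a contact that supplies the date.

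On weight, the trial describes itself as exploratory, OS carries no hypothesis or comparison, and with all deaths reported the illustrated error lies within one standard error. The -3.5 end needs a 2-month median time to progression, the 7-week last contact and the 18-month cut-off together. All of that is fair.

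A reader might infer three stronger things that the documents do not support:
- *That progressed survivors will have no later alive date.* Section 7.2 may well produce one. The documents show only that none is scheduled.
- *That OS will be overstated through missed deaths.* Death Reports are required for all patients, and no text supports any particular rate of non-reporting. The positive errors above are conditional on assumed rates.
- *That every survivor is affected.* At the cited rates 0.67 × 84 = 56 patients would be alive at 1 year, but the gap concerns only those who have progressed and passed their last required contact.

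**Conclusion.** The point holds and should be fixed. The plan gives no OS censoring rule for patients alive after progression. It also does not say whether the waiver in 9.2, Appendix I footnote 8 and Appendix IV leaves the survival follow-up of 7.2 in force. Since deaths are reported on knowledge while later survival is not scheduled to be recorded, OS censoring may be informative.

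The documents fix neither the size nor the direction. The illustration suggests a modest downward error at 12 months if death reporting is complete as required, and none if vital status is complete to a common cut-off. Those figures rest on the assumed progression and post-progression survival pattern, the assumed cut-offs, and Kaplan-Meier estimation, which Section 14 does not name; they are not a forecast for this trial. The consequence is limited to OS and to the survival input of the Section 14.4 model. The primary analysis of texture against response is untouched.

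**What to change.** 1. In Section 9.2, Appendix I footnote 8 and Appendix IV, state that the waiver after progression and the 1-year cap apply to visits and investigations, not to survival status, consistent with Section 7.2.
2. Make one vital-status sweep of all patients, by chart or telephone, at a common data cut-off. Record the date of death or the date last known alive.
3. Add to Section 10.8 that OS is censored at the date last known alive, or at the cut-off if earlier, whatever the progression status.

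Cost: one clarifying sentence in each of three places, one sentence in 10.8, and one status check of at most 84 patients. No added clinic visit or scan is needed.

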10.0 CRITERIA FOR MEASUREMENT OF STUDY ENDPOINTS

10.1 Definitions

10.1.1 Evaluable for adverse events. All patients will be evaluable for adverse event evaluation from the time of their first treatment.

10.1.2 Evaluable for response. All patients who have received at least one cycle of therapy and have their disease re-evaluated will be considered evaluable for response (exceptions will be those who exhibit objective disease progression prior to the end of cycle 1 who will also be considered evaluable). Patients on therapy for at least this period and who meet the other listed criteria will have their response classified according to the definitions set out below [Seymour 2016].

Response and progression will be evaluated in this study using the revised international criteria (1.1) proposed by the RECIST (Response Evaluation Criteria in Solid Tumours) committee as well as the modified iRECIST guidelines [Seymour 2016]. Investigators should note the different requirements for confirmatory scans as well as follow up for the two criteria.

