8.1 Chemotherapy Treatment Plan

8.1.1 Drug Administration

Agent	Route	Starting Dose	Schedule
Pembrolizumab	IV	200 mg	Day 1 every 3 weeks

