9.1 Evaluation During Protocol Treatment

	Investigations	Timing
History and Physical Exam including:	
 history weight ECOG Performance status vital signs (blood pressure and pulse) clinical tumour measurements (if applicable) 	Day 1 each cycle
Hematology*	
 CBC, differential, platelets 	Day 1 each cycle
Biochemistry*	
 electrolytes (sodium, potassium, chloride, bicarbonate) alkaline phosphatase AST, ALT serum creatinine bilirubin 	Day 1 each cycle
	
 phosphorous calcium magnesium albumin 	As clinically indicated
	
 TSH, FT3, FT4 	Every other cycle
Radiology**	
 CT scan with contrast of chest, abdomen/pelvis Other sites as clinically indicated 	4 weeks, 12 weeks, then every 12 weeks
Other Investigations	
 ECG 	As clinically indicated
Economics	
 Health Utilities Index (EQ-5D) Resource Utilization Assessment 	To be completed at each 12 weekly visit until progression OR maximum 1 year from registration
Adverse Events***	Patients must be evaluated after each cycle for adverse events	

* Bloodwork Timing: Pre-treatment blood draws should be done within 72 hours (maximum) prior to treatment.

** Patients with a CR or PR should have scans repeated after minimum 4 weeks to confirm response. See Appendix VII for CT requirements.

*** Adverse events will be recorded and graded according to the NCI Common Terminology Criteria for Adverse Events (CTCAE) (Appendix V).

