Target Lesions	Non-Target Lesions	New Lesions	Overall Response	Best Response for this Category also Requires
Target lesions ± non target lesions				
CR	CR	No	CR	Normalization of tumour markers, tumour nodes <10mm
CR	Non-CR/Non-PD	No	PR	
CR	Not all evaluated	No	PR	
PR	Non-PD/ not all evaluated	No	PR	
SD	Non-PD/ not all evaluated	No	SD	documented at least once \geq 4 wks. from baseline
Not all evaluated	Non-PD	No	NE	
PD	Any	Any	PD	
Any	PD	Any	PD	
Any	Any	Yes	PD	
Non target lesions ONLY				
No Target	CR	No	CR	Normalization of tumour markers, tumour nodes < 10mm
No Target	Non-CR/non-PD	No	Non-CR/non-PD	
No Target	Not all evaluated	No	NE	
No Target	Unequivocal PD	Any	PD	
No Target	Any	Yes	PD	
Note: Patients with a global deterioration of health status requiring discontinuation of treatment without objective evidence of disease progression at that time should be reported as "symptomatic deterioration". This is a reason for stopping therapy, but is NOT objective PD. Every effort should be made to document the objective progression even after discontinuation of treatment.				

Immune-Related Response Assessment

Overall response will also be assessed using iRECIST [Seymour 2016]. Immunotherapeutics may result in infiltration of immune cells leading to transient increase in the size in malignant lesions, or undetectable lesions becoming detectable. The criteria are identical to those of RECIST 1.1 in many respects but have been adapted to account for instances where an increase in tumour burden, or the appearance of new lesions, does not reflect true tumour progression.

Key differences are described below. All responses defined using iRECIST criteria are designated with a prefix. iRECIST time-point and best overall responses will be recorded separately.

AMEND #1: 2016-NOV-23

Confirming Progression

Unlike RECIST 1.1, iRECIST requires the confirmation of progression and uses the terms iUPD (unconfirmed progression) and iCPD (confirmed progression). Confirmatory scans should be performed at least 4 weeks, but no longer than 8 weeks after iUPD.

iCPD is confirmed if further increase in tumour burden, compared to the last assessment, is seen as evidenced by one or more of the following:

- Continued increase in tumour burden (from iUPD) where RECIST 1.1 definitions of progression had been met (from nadir) in target, non-target disease or new lesions
 - Progression in target disease worsens with an increase of at least 5 mm in the absolute value of the sum

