- 10.5.5 **Endoscopy, Laparoscopy**. The utilization of these techniques for objective tumour evaluation is not advised. However, they can be useful to confirm complete pathological response when biopsies are obtained or to determine relapse in trials where recurrence following complete response or surgical resection is an endpoint.
- 10.5.6 **Tumour Markers**. Tumour markers alone cannot be used to assess objective tumour response. If markers are initially above the upper normal limit, however, they must normalize for a patient to be considered in complete response.
- 10.5.7 **Cytology, Histology**. These techniques can be used to differentiate between PR and CR in rare cases if required by protocol (for example, residual lesions in tumour types such as germ cell tumours, where known residual benign tumours can remain). When effusions are known to be a potential adverse effect of treatment (e.g. with certain taxane compounds or angiogenesis inhibitors), the cytological confirmation of the neoplastic origin of any effusion that appears or worsens during treatment when the measurable tumour has met criteria for response or stable disease is advised to differentiate between response or stable disease and progressive disease.

10.6 **Time to Tumour Progression**

Time to tumour progression will be measured from date of registration until documented progression or death.

10.7 **Overall Survival**

Overall survival will be calculated from date of registration until death.

10.8 **Censoring**

Patients alive without progression at end of study will be censored at last visit/known to be alive and progression free.

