14.2 Sample Size and Duration of Study

This is the first trial to evaluate tumour texture parameters to correlate them with tumour response to pembrolizumab.

Without knowing the true fraction of patients with CT features that are considered “positive” or “negative” it is not possible to do a true power calculation and the trial should be viewed as exploratory assessment of the potential of texture parameters to correlate with response. However, assuming the response rate to pembrolizumab is 35%, then a sample size of 80 patients will allow analysis of CT texture analysis parameters among 20-25 responding patients versus 55-60 non-responding patients. We propose to recruit 84 patients to identify 80 evaluable patients to assess for texture parameters in responders and non-responders which may support further evaluation in definitive trials. Sensitivity, specificity, positive and negative predictive values will be assessed.

Accrual rate is anticipated to be approximately 5-10 patients/month for total duration of accrual of 6-12 months.

Patients will be followed on study for the duration as indicated in Section 12.

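### Treated patients who die or deteriorate and are never re-imaged are non-evaluable under Section 10.1.2 rather than non-responders, so early failures drop selectively out of the response-based analyses

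*Combined protocol and SAP*

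**What the plan says.** Section 10.1.2 sets the condition for entering the response assessment: "All patients who have received at least one cycle of therapy and have their disease re-evaluated will be considered evaluable for response". It has one exception: "exceptions will be those who exhibit objective disease progression prior to the end of cycle 1 who will also be considered evaluable". Response is then classified for patients who meet these conditions. Death before a scan is not mentioned.

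The note to Table 1 in Section 10.2.5 says of symptomatic deterioration: "This is a reason for stopping therapy, but is NOT objective PD". It adds: "Every effort should be made to document the objective progression even after discontinuation of treatment".

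Treatment is given "Day 1 every 3 weeks" (Section 8.1.1) and on-treatment CT is scheduled at "4 weeks, 12 weeks, then every 12 weeks" (Section 9.1). The first planned re-evaluation thus falls a week after cycle 1 ends.

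Section 14.2 ties the texture comparison to evaluability: "We propose to recruit 84 patients to identify 80 evaluable patients to assess for texture parameters in responders and non-responders". It does not refer to 10.1.2. Section 14 defines no all-treated set, gives no rule for unscanned patients and plans no sensitivity analysis.

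Two other places bear on the point. The opening of Section 10.2.5 has the best response of every patient classified, but Table 1 has no category for death before a scan. Section 10.6 counts death as an event: "Time to tumour progression will be measured from date of registration until documented progression or death".

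**The concern.** The exclusion depends on the outcome. The patients removed are treated patients whose disease or death prevented a second scan, and all of them belong on the non-responder side. They should normally have a contrast CT from before registration (Sections 5.1.2 and 6.0), so a baseline texture value can usually be obtained.

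The primary objective is to see whether texture separates responders from non-responders. Section 2.0 gives the intended uses as selecting patients for treatment and stopping early when treatment fails. Early failures are the cases such a marker should detect, so accuracy measured without them may not describe the population in which it would be used. A response rate computed without them is too high.

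**Working it through.** **1. Who is lost.**

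| Treated patient | Status under 10.1.2 |
|---|---|
| Objective progression before the end of cycle 1 | Evaluable, by the exception |
| Deteriorates or stops, but is scanned later | Evaluable after at least one cycle; 10.1.2 sets no latest date for re-evaluation |
| Dies without any post-baseline imaging or objective progression | Not evaluable |
| Stops for symptomatic deterioration, never re-imaged, no objective progression | Not evaluable; the Table 1 note rules out the exception |

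The second row is a real route. Section 9.2 asks for CT at least every 3 months, until progression or for at most 1 year, in patients who stop before documented progression. Appendix I also marks CT in the column for 4 weeks post treatment.

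**2. The plan's own figures.** Section 14.2 assumes a 35% response rate in 80 patients: 0.35 × 80 = 28 responders and 52 non-responders. It states 20–25 and 55–60, which corresponds to 25.0–31.3%. That mismatch is a separate matter, so results are given for both. The allowance for non-evaluable patients is 84 − 80 = 4.

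**3. Response rate.** Let R be the number of responders and m the number of excluded failures. The rate is R/(84 − m) by the rule and R/84 among all treated (taking all 84 as treated). The difference, R·m / [84(84 − m)], is never negative. With m = 4, assuming that all four are unscanned failures:

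| R | By the rule | All 84 | Difference |
|---|---|---|---|
| 28 | 28/80 = 35.0% | 28/84 = 33.3% | 1.7 points |
| 25 | 25/80 = 31.3% | 25/84 = 29.8% | 1.5 points |
| 20 | 20/80 = 25.0% | 20/84 = 23.8% | 1.2 points |

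With R = 28 there are 84 − 28 = 56 non-responders in all, of whom 4/56 = 7.1% are lost. If none of the four is such a failure, this mechanism produces no bias.

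**4. Accuracy measures.** The documents define no texture cut-off. For illustration, call a predicted responder texture-positive and assume a specificity of 39/52 = 75% in the evaluable set. Adding the four failures gives:

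- all four texture-positive: 39/56 = 69.6%;
- all four texture-negative: (39 + 4)/56 = 43/56 = 76.8%.

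Sensitivity does not change, because no responders are added. A texture-positive failure lowers PPV and leaves NPV alone; a texture-negative failure raises NPV and leaves PPV alone. For scale, assume sensitivity and specificity of 70% with 28 responders and 52 non-responders. The expected counts are 19.6 true positives, 8.4 false negatives, 36.4 true negatives and 15.6 false positives.

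- PPV: 19.6/35.2 = 55.7%, falling to 19.6/39.2 = 50.0% if all four are positive.
- NPV: 36.4/44.8 = 81.25%, rising to 40.4/48.8 = 82.8% if all four are negative.

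**5. Is four plausible?** The documents give no early-death rate. Section 2.0 cites 1-year survival of 67% and 74% with pembrolizumab. Under an assumed constant hazard, deaths by week 4 among 84 are 84 × (1 − 0.67^(4/52)) = 2.5 and 84 × (1 − 0.74^(4/52)) = 1.9. Deterioration without a scan would add to this; entry restricted to ECOG 0–1 could make early deaths fewer.

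**The case against.** **The denominators are inferred.** No passage states the denominator of the response rate. Section 10.2.5 speaks of every patient, and evaluable in 14.2 could mean having a usable texture scan. This stands in part. The 10.1.2 set is the natural reading, since it is the only definition of response evaluability, but it is a reading. The conflict is itself a reason to settle the wording.

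**The group is small.** A reader might infer that everyone who dies or deteriorates before the week-4 CT is lost. The documents do not support that: early objective progressors are kept, the Table 1 note urges documentation of progression after stopping, and later scans count. Only patients never re-imaged, and without early objective progression, drop out.

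**The effect is small and no decision turns on it.** The largest shift within the plan's allowance is 1.7 points, against an exact 95% interval of 24.7% to 46.5% for 28/80. Section 14.2 calls the trial exploratory. This stands, and limits the weight of the point; it does not justify exclusion by outcome.

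**The texture time point is not named.** Appendix VI schedules texture CT at baseline and on treatment, and Section 14.2 does not say which scan carries the comparison. This stands. Unscanned patients can be restored only to an analysis of baseline texture.

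**Section 10.6 is not in contradiction.** A reader might infer an inconsistency because a death is an event for time to progression but missing from response. That is an ordinary difference between endpoint types. It shows only that these patients remain in one texture objective while leaving the other.

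**Conclusion.** The point holds. As written, 10.1.2 removes treated patients who die or deteriorate without ever being re-imaged, and 14.2 most naturally carries that exclusion into the primary texture comparison. Sections 10.1.2, 10.2.5 and 14.2 must be reconciled.

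The effect on the response rate can only be upward. It is at most 1.7 points (35.0% against 33.3%) with 28 responders if all 4 allowed non-evaluable patients are such failures, and less if fewer are. Selective loss from the primary comparison matters more than this shift. A reader might infer that the marker's accuracy is flattered throughout; the documents do not support that. The direction for specificity is unknown (69.6% to 76.8% around an assumed 75%), and whether PPV or NPV changes depends on the lost patients' texture results. Time to progression and overall survival are unaffected. For an exploratory trial this should be corrected, but it does not undermine the design.

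**What to change.** - **Sections 10.1.2 and 10.2.5:** make all eligible patients who received at least one dose the response-rate denominator. Class death or symptomatic deterioration without any post-baseline scan as non-response, both for the response rate and for the comparison using baseline texture.
- **Stopping for toxicity without a scan:** count these patients in the response-rate denominator as not responding. Their true response is unknown, so handle them in the texture comparison by a sensitivity analysis.
- **Section 14.2:** treat a patient as non-evaluable for baseline texture only if there is no usable baseline texture scan, and name the scan used in each texture analysis. On-treatment texture analyses necessarily remain limited to scanned patients.
- **Sensitivity analysis:** repeat the response rate and the texture comparison in the current 10.1.2 evaluable set.

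Settle these rules before the central texture reading in Section 13.1. The cost is wording only: baseline CT is required for entry, and Death Reports are required for all patients (Section 9.2 and Appendix IV). The downside is a slightly less favourable response rate.
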